**Open-Label Extension Study Visit (up to 12 additional visits) to occur monthly (+/- 1 week)**

**\*Visits may be conducted virtually due to the Covid-19 outbreak.**

Collect physical examination results

Collect Vital Signs measurement results

Collect most recent Chemistry Panel results approximately every 3 months (sodium, potassium, chloride, bicarbonate, blood urea nitrogen, creatinine glucose)

Collect Liver Function test results approximately every 3 months (total bilirubin, direct bilirubin, alkalkine phosphatase, alanine

aminotransferase, aspartate aminotransferase, lipase, amylase)

Collect Serum pregnancy test results every 3 months if completed

Monitor severe adverse events (SAE) and adverse events (AE)

Collect Concomitant medications

Collect Nutritional Assessment if completed

Collect approximate daily average fistula volume

Collect adjustment of medications and fluids if recorded

**Open-Label Extension Telephone Visit to occur every 2 weeks (+/- 3 days) alternating with Open-Label Extension Study Visits**

Monitor severe adverse events (SAE) and adverse events (AE)

Collect Concomitant medication review

Collect Nutritional Assessment

Collect approximate daily average fistula volume

Collect adjustment of medications and fluids if recorded

**Drug Administration, Dispensation and Disposition**

Once consent is obtained and necessary baseline data collected, the subject will begin receiving teduglutide (0.05 mg/kg/d, for moderate renal impairment defined as serum

IRB Study Number: 20170189  
Version Date: June 16, 2021  
PI: [name]

NCT02889393

creatinine > 1.5 times the upper limit of normal, the dose will be reduced to 0.025 mg/kg/d, administered once daily subcutaneously into the abdomen, thigh, or arm (at approximately the same time each day) for 8 weeks. For enrolled subjects demonstrating a favorable trend and are deemed to be reliable (both as determined by the PI) but still have a fistula at the end of treatment (EOT) or long-term follow-up, the subject will be offered an “open-label” extension whereby they will continue to receive teduglutide at the previous dose for up to another 12 months or permanent fistula closure, whichever occurs first.

Immediately prior to initiating the 8-week period of drug administration, the subject will receive training on how to safely reconstitute and administer the medication. The volume of reconstituted study drug to be administered is a fixed dose of 0.005 mL/kg body weight. Each day, the injection site should be changed. The subject should be dosed at approximately the same time each day. If a subject forgets to take drug, that day’s dose should be administered as soon as possible, even if this is later in the day or evening. Consecutive doses should be separated by approximately 12 hours. Dates of days with missed or incomplete doses are to be reported in the diary. The subject is going to be instructed to bring back all used and unused IP. The IP will then be disposed of per pharmacy SOP. University of Miami Research Pharmacy will be receiving, storing, dispensing, keeping inventory, and disposing the IP for this study as per their standard operating procedures.

Study drug will be packaged, labeled, and delivered to the clinical center by the sponsor or designee. Each study drug kit will contain labeling with the general dosage instructions, storage conditions, expiration date, kit number, and company name. All medication supplied to be used in this study will be manufactured, tested, labeled, and released according to current legal requirements and Good Manufacturing Practice (GMP). Ancillary supply kits containing syringes with needles for injection and reconstitution, sterile water, and alcohol swabs will also be provided.

The Principle Investigator or designee will conduct an inventory upon receipt of the clinical supplies and will acknowledge receipt of the supplies to the sponsor. A copy of the shipping documents will be maintained for records. Study drug will be kept at controlled room temperature (15°-25°C, 59°-77°F) in a secure location until dispensed to the subject. Subjects will be instructed to keep study drug at controlled room temperature. The sterile water diluent should be stored at controlled temperature.

Study drug kits will be dispensed to subjects at each of the office visits during the 8 weeks of dosing and up to an additional 52 weeks of “open-label” extension at which the subject is required to be at the clinic. Each study drug kit is sufficient for a treatment period of 4 weeks (depending on visit #). The PI will keep a current record of the inventory and dispensing of all clinical supplies. This record will be made available to the sponsor’s monitor for the purpose of accounting for all clinical supplies. Any discrepancy or deficiency will be recorded, with an explanation. All supplies sent to the investigator will be accounted for and in no case will clinical supplies be used in an unauthorized situation.

IRB Study Number: 20170189  
Version Date: June 16, 2021  
PI: [name]

NCT02889393

Subject compliance will be checked at every visit (and telephone call) by asking the subjects if they have taken their study drug according to instructions and by reviewing the subject diary if available and to perform drug accountability. Compliance is considered to be achieved if the subject reports (by diary or discussion) 80% of the planned doses administered. The hierarchy of source documentation is the Diary as primary, and if not available then followed by study staff documentation of weekly visits and lastly documentation of monthly visits.

At present, the standard of care (SOC) for ECF involves source control treatment of intra-abdominal infection, nutritional support via enteral nutrition (EN), parenteral nutrition (PN), or oral intake, careful fluid and electrolyte management, and occasionally surgical repair. Subjects enrolled in this study will still receive SOC in addition to 8 weeks of teduglutide therapy and up to an additional 52 weeks of open-label extension when this applies.

Unless contraindicated by clinical condition, enrolled patients will undergo colonoscopy within 6 months prior to starting the drug.

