**Design**

Open label cross-over pilot study to determine safety and efficacy of teduglutide in patients with ECF. Our planned sample size is 10 subjects randomized and treated with at least 1-dose of study drug .

IRB Study Number: 20170189  
Version Date: June 16, 2021  
PI: [name]

NCT02889393

The primary efficacy end point will be decrease in fistula volume by 20% from baseline 3-day average, as measured by the patient.

The secondary efficacy end points will be cessation of fistula output altogether and health-related quality of life questionnaire score as assessed by the questionnaires (see below) at time points Study Visit 5, 10, and 11 (3 months after end-of-treatment).

Subjects that complete both arms of the study who have a favorable (but incomplete) response and are deemed to be reliable (both as determined by the principal investigator) will be offered an open-label extension during which they will continue to receive teduglutide for up to another 12 months or permanent fistula closure, whichever occurs first.

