##### **Exclusion criteria**

- a) Perianal fistula
- b) History of radiation enteritis or sprue (as defined by history)
- c) Active (<1 year) alcohol or drug abuse
- d) Significant hepatic, or cardiac diseases as defined as:
  - i. Hepatic: aspartate aminotransferase (AST)  $\geq 2$  times upper limit of normal (10-40 U/L)
  - ii. Cardiac: unstable angina or evidence of active myocardial ischemia (elevated troponin level drawn by clinical suspicion)
- e) Severe renal dysfunction: serum creatinine  $\geq 2$  times upper limit of normal (0.6-1.5 mg/dL)
- f) Received IV glutamine less than 4 weeks prior to screening
- g) Receiving growth factors (erythropoietin, granulocyte colony-stimulating factor, granulocyte-macrophage colony stimulating factor, and human growth hormone)
- h) Pregnancy or lactation (women of childbearing age will be excluded if they do not agree to either complete sexual abstinence during the study or if they refuse to use at least two forms of highly effective contraception such as oral contraception, injectable or implantable contraception, vaginal rings, or intrauterine devices (IUD))
- i) Active malignancy or suspicion for gastrointestinal malignancy on CT scan obtained during standard clinical care, if available
- j) Not capable of understanding or not willing to adhere to the study visit schedule and drug administration requirements

IRB Study Number: 20170189  
Version Date: June 16, 2021  
PI: [name]

NCT02889393

- k) First degree relative with history of intestinal malignancy (gastric, small intestine, colon)
- l) Personal or first degree relative with history of hereditary non-polyposis colorectal cancer, familial adenomatous polyposis, first degree relative with colon cancer
- m) Positive hemoccult (per rectum) obtained during standard clinical care, if available
- n) Abnormal baseline electrocardiogram (ECG) suggestive of congestive heart failure or underlying cardiac disease
- o) Taking oral benzodiazepines, barbiturates, or phenothiazines

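### One fixed injection volume per kg cannot deliver both stated doses; at the concentration implied by the standard dose, it gives renally impaired subjects twice their reduced dose

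*Combined protocol and SAP*

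**What the plan says.** All the dosing rules are in section 5, under Drug Administration, Dispensation and Disposition. The standard dose appears in "the subject will begin receiving teduglutide (0.05 mg/kg/d, for moderate renal impairment defined as serum" creatinine above 1.5 times the upper limit of normal. For that group "the dose will be reduced to 0.025 mg/kg/d, administered once daily subcutaneously".

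The next paragraph, on training subjects to reconstitute and inject the drug themselves, gives the only injection volume in the protocol: "The volume of reconstituted study drug to be administered is a fixed dose of 0.005 mL/kg body weight". It is described as fixed and makes no exception for the reduced dose.

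Three other provisions bear on the point:

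- **Eligibility.** The Exclusion criteria bar subjects whose creatinine is at least 2 "times upper limit of normal (0.6-1.5 mg/dL"). Subjects between 1.5 and 2 times the limit may therefore enter.
- **Supply.** The kit description makes no distinction by dose level: "Each study drug kit is sufficient for a treatment period of 4 weeks". No vial strength, diluent volume or reconstituted concentration is given.
- **Extension.** Subjects who respond incompletely may go on, and "they will continue to receive teduglutide at the previous dose for up to another 12 months or permanent fistula closure".

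**The concern.** A dose in mg/kg and a volume in mL/kg together fix a concentration. Two doses with one volume fix two different concentrations, so the volume rule must be wrong for one dose level unless the drug comes in two strengths, and the protocol mentions no second strength.

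Volume is what the subject actually measures. If the one stated volume is used for a subject assigned the reduced dose, the renal reduction is cancelled. The protocol would not readily reveal this. Compliance is judged by the share of planned doses reported as taken (80% is the threshold), so a subject drawing twice the intended volume every day would count as fully compliant. An unnoticed error could run through the 8 weeks of treatment and into the extension.

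Safety is one of the trial's stated objectives, and it was the protocol itself that judged half the dose appropriate for these subjects.

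**Working it through.** **Inputs from the protocol**

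- Standard dose 0.05 mg/kg/d; reduced dose 0.025 mg/kg/d; volume 0.005 mL/kg (Drug Administration, Dispensation and Disposition).
- Dose reduction above 1.5 times the upper limit (same section); exclusion from 2 times the upper limit (Exclusion criteria).
- Upper limit of normal for creatinine 1.5 mg/dL (Exclusion criteria; also section 6, Data and Specimen Banking).

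The 0.005 mL/kg figure cannot be reproduced independently, because no concentration is stated. It can only be converted into the concentration that each dose would require.

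**Step 1: implied concentration = dose per kg / volume per kg**

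- Standard: 0.05 / 0.005 = 10 mg/mL.
- Reduced: 0.025 / 0.005 = 5 mg/mL.

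The two differ, so one concentration cannot satisfy both.

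**Step 2: dose delivered = volume per kg × concentration**

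| Assumed concentration | Delivered by 0.005 mL/kg | Against 0.05 mg/kg | Against 0.025 mg/kg |
|---|---|---|---|
| 10 mg/mL | 0.05 mg/kg | correct | 2 times too high |
| 5 mg/mL | 0.025 mg/kg | half | correct |

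The 10 mg/mL row is the more natural reading, since the volume then matches the standard dose. At that concentration the reduced dose needs 0.025 / 10 = 0.0025 mL/kg.

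**Step 3: amounts per day at 10 mg/mL (body weights are assumed)**

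| Weight | Volume by the stated rule | Dose given | Dose intended | Volume needed |
|---|---|---|---|---|
| 50 kg | 0.25 mL | 2.5 mg | 1.25 mg | 0.125 mL |
| 70 kg | 0.35 mL | 3.5 mg | 1.75 mg | 0.175 mL |
| 90 kg | 0.45 mL | 4.5 mg | 2.25 mg | 0.225 mL |

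At 70 kg over the 56 treatment days: 56 × 3.5 = 196 mg given, against 56 × 1.75 = 98 mg intended. A full 52-week extension with the error uncorrected would add an excess of 364 × 1.75 = 637 mg.

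**Step 4: can a reduced-dose subject enrol?**

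- Reduction applies above 1.5 × 1.5 = 2.25 mg/dL.
- Exclusion applies from 2 × 1.5 = 3.0 mg/dL.

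Creatinine above 2.25 and below 3.0 mg/dL is therefore eligible and assigned the reduced dose.

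**Step 5: how likely is such a subject among 10?**

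The protocol gives no prevalence. With an assumed share p of enrolled subjects in this range, the chance of at least one is 1 − (1 − p)^10:

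- p = 2%: 18%.
- p = 5%: 40%.
- p = 10%: 65%.

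This is the chance of enrolling someone assigned the reduced dose, not the chance that someone is misdosed.

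**The case against.** The strongest reply is that the prescribed dose is clear. The mg/kg sentence governs, and the volume sentence reads naturally as the standard-dose volume with the renal case left out. For harm to follow, staff would have to assign the reduced dose and then set the full-dose volume. Individual training, the research pharmacy's own procedures, kit labelling and the Medication Guide all stand in between. Their contents are not in the document, so they may already give the right volume. Even in the worst case the subject receives the trial's own standard dose, with fluid-overload monitoring and laboratory checks in place. The extension carries an error forward only if one has already occurred unnoticed, and the body weights and prevalences above are assumptions.

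Much of this stands as a limit on the consequence. An actual overdose is not shown, the number affected may be zero, and the 5 mg/mL case is the less plausible one. Two product strengths would also reconcile the text, though none is described.

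It does not remove the contradiction. If the volume sentence covers only the standard dose, the reduced dose has no volume instruction at all and the same correction is needed. Material outside the protocol cannot make the protocol consistent. The monitoring rules look for symptoms and abnormal results; they would not themselves correct a wrong volume.

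**Conclusion.** The concern holds. As written, the volume rule contradicts one of the two dose levels. If the reconstituted concentration is the 10 mg/mL implied by the standard dose, following the rule gives exactly twice the intended dose to subjects with creatinine above 2.25 and below 3.0 mg/dL. The factor of two depends only on that concentration, which the sponsor must confirm; the milligram totals also depend on assumed body weights. If the concentration were 5 mg/mL, the error would move to every standard-dose subject, who would receive half the stated dose.

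This is a patient-safety error in the dosing instruction and must be fixed, even though few or none of the 10 subjects may be affected. The primary endpoint analysis does not depend on it.

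**What to change.** State the reconstituted concentration and give one injection volume for each dose level. If the sponsor confirms 10 mg/mL:

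- 0.05 mg/kg/d: 0.005 mL/kg (0.35 mL at 70 kg).
- 0.025 mg/kg/d: 0.0025 mL/kg (0.175 mL at 70 kg).

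If two strengths are in fact supplied, name both and say which goes with which dose. Then check that the pharmacy procedure, kit labelling, subject training and Medication Guide carry the correct volume for each dose level, including in the extension.

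The cost is a one-line protocol amendment and a review of the pharmacy and patient instructions. Design, sample size and analysis do not change.

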### **Enrollment within 2 months of signing consent**

Inclusion/Exclusion criteria

Vital signs measurements

Nutritional assessment

3-day average fistula output

Complete questionnaires (see additional documents):

1. ASCQ-Me Short Form v2.0 - Social Functioning Impact
2. ASCQ-Me v2.0 - Sleep Impact Short Form

IRB Study Number: 20170189  
Version Date: June 16, 2021  
PI: [name]

NCT02889393

3. Global Health Scale v1.2
4. PROMIS Scale v1.0 - GI Belly Pain
5. PROMIS Scale v1.0 - GI Diarrhea
6. PROMIS Scale v1.0 - GI Nausea and Vomiting
7. PROMIS SF v2.0 - Ability to Participate

Teaching of self-administration of medication

After study enrollment, the subject will be randomly assigned (by a computerized method, using the site 'www.sealedenvelope.com') to begin teduglutide treatment immediately or to continue standard of care (SOC) treatment. The randomization will be performed by a member of the study that is not involved in the informed consent process, and will be enclosed in sequentially numbered opaque envelopes. The envelopes will be given to the PI prior to the enrollment visit. At study visit 5 (day 56), the subject will then cross-over to the opposite treatment assignment. The half-life of teduglutide is 2-3 hours. During the period the subjects are on the "SOC only" treatment arm, the subjects will be given the option to replace some Study visits with Telephone Calls for their convenience. If study visits overlap due to the time window, either visit may be skipped or completed on the same day. Please see information below, and the Study schema.

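### The dosing paragraph prescribes one injection a day but spaces consecutive doses about 12 hours apart; a minimum gap after a late dose was almost certainly meant (minor wording fix)

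*Combined protocol and SAP*

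**What the plan says.** All the dosing instructions are in section 5, under Drug Administration, Dispensation and Disposition. The drug is to be "administered once daily subcutaneously into the abdomen, thigh, or arm (at approximately the same time each day) for 8 weeks", at 0.05 mg/kg/d, or 0.025 mg/kg/d in moderate renal impairment. The next paragraph repeats the timing rule: "The subject should be dosed at approximately the same time each day". For a forgotten injection, that day's "dose should be administered as soon as possible, even if this is later in the day or evening". The sentence at issue follows immediately: "Consecutive doses should be separated by approximately 12 hours".

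The neighbouring instructions also assume a daily schedule: "Each day, the injection site should be changed" and "Dates of days with missed or incomplete doses are to be reported in the diary". No other part of the document gives a dosing interval or mentions twice-daily dosing.

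**The concern.** One dose a day at a fixed clock time means about 24 hours between doses, and the sentence gives half that. It sets a target, where a floor would have been consistent with everything around it. It also applies to all consecutive doses, although its position suggests it was written for late ones.

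Subjects are trained to inject themselves for 8 weeks, and those who enter the extension continue for up to another 12 months. If a dose is a few hours late, the same-time rule sends the subject back to the usual hour, while this sentence points to a time several hours earlier, possibly the same day. What is at stake is an occasional extra or mistimed injection. The efficacy comparison does not depend on it.

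**Working it through.** **Inputs from the protocol.** One dose a day, 0.05 mg/kg/d (0.025 in moderate renal impairment), 8 weeks = 56 days, and the 12-hour spacing, all from Drug Administration, Dispensation and Disposition. The enrollment subsection of section 5 states: "The half-life of teduglutide is 2-3 hours".

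**Assumptions.** A usual dosing time of 08:00; a combined tolerance of 1, 2 or 4 h for the two approximate timing rules; first-order decay for the residual drug.

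**1. Routine spacing.** Doses per day = 24 / interval in hours.

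| | Once daily | Literal 12 h |
|---|---|---|
| Doses per day | 24/24 = 1 | 24/12 = 2 |
| Doses in 56 days | 56 | 112 |
| Daily dose (mg/kg) | 0.05 | 0.10 |
| Daily dose, renal reduction (mg/kg) | 0.025 | 0.05 |

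Both cannot be the routine schedule. The once-daily column matches every other instruction in the subsection.

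**2. Read only as a late-dose rule.** Let c be the clock hour of the late dose and L = c − 8 its lateness. The 12-hour target is c + 12, and the next usual time is hour 32 (08:00 next day). Target minus usual time = (c + 12) − 32 = L − 12. The last column is the next dose if 12 hours were a minimum: max(32, c + 12).

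| Late dose taken | Target under current sentence | Target minus usual time | Next dose if 12 h is a minimum |
|---|---|---|---|
| 10:00 | 22:00 same day | −10 h | 08:00 |
| 12:00 | 00:00 | −8 h | 08:00 |
| 16:00 | 04:00 | −4 h | 08:00 |
| 18:00 | 06:00 | −2 h | 08:00 |
| 20:00 | 08:00 | 0 h | 08:00 |
| 22:00 | 10:00 | +2 h | 10:00 |
| 23:00 | 11:00 | +3 h | 11:00 |

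**3. When both rules can be met.** This needs |12 − L| ≤ t, where t is the combined tolerance.

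- t = 1 h: 11 to 13 h late (19:00 to 21:00)
- t = 2 h: 10 to 14 h late (18:00 to 22:00)
- t = 4 h: 8 to 16 h late (16:00 to 24:00)

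So the conflict lies with on-time doses and with doses less than about 8 to 11 h late. From 20:00 onward the current sentence and a 12-hour minimum give the same next time.

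**4. How much of the earlier dose remains.** Residual = 0.5^(gap / half-life). The 10 h and 9 h gaps are those left when a 22:00 or 23:00 dose is followed by one at 08:00.

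| Gap | Half-life 2 h | Half-life 3 h |
|---|---|---|
| 12 h | 0.5^6 = 1.6% | 0.5^4 = 6.3% |
| 10 h | 0.5^5 = 3.1% | 0.5^3.33 = 9.9% |
| 9 h | 0.5^4.5 = 4.4% | 0.5^3 = 12.5% |

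Little of the earlier dose is left at these gaps. That says nothing about how long its effect lasts.

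**5. Would an error be noticed?** The Appendix E schema puts drug accountability at enrollment and days 7, 14, 28, 42 and 56 in the first period, and at days 56, 63, 70, 84, 98 and 112 in the second. The nominal gaps are 7, 7, 14, 14 and 14 days in each. Extension visits are monthly. Returned drug would probably reveal extra doses. The numerical compliance criterion would not reveal timing, because it counts doses: "Compliance is considered to be achieved if the subject reports (by diary or discussion) 80% of the planned doses administered".

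**The case against.** The strongest reply is that the meaning is clear from context. The sentence comes directly after the forgotten-dose rule, the once-daily order is explicit, and the same-time rule appears twice. Few readers would take a second injection at 22:00 after one at 10:00, and for evening doses, the latest case the protocol names, the sentence works as intended.

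The safeguards are also substantial. Staff ask about adherence to the dosing instructions at every visit and telephone call, which is weekly in the 8-week treatment period and about every two weeks in the extension. Those questions can bring out a timing error that the 80% criterion misses. The Appendix E schema provides for repeat teaching of self-administration, if needed, at nearly every contact. Section 9 records an overdose as an adverse event even without symptoms. The kit labels and the Medication Guide are not reproduced, so subjects may never see this sentence.

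All of this stands, and it is why the point is minor. It bears on how likely harm is. It does not make the sentence correct: a dose a few hours late is an ordinary case for the forgotten-dose rule, and there the words point to the wrong time. The clock times and tolerances are illustrative, and the contradiction does not depend on them.

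**Conclusion.** The sentence is wrong as written and should be corrected; severity is minor. It conflicts with once-daily dosing for on-time doses and for doses less than about 8 to 11 hours late, the exact bound depending on the assumed tolerance. That a minimum gap was intended is an inference, but every neighbouring instruction supports it. The likely consequence is limited to an occasional extra or mistimed self-injected dose. Routine doubling to 112 doses is what the literal words imply, not what should be expected. No endpoint, sample size or analysis changes. Whether the sentence reaches subjects through training or labels cannot be determined from the protocol.

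**What to change.** The smallest adequate change is to replace 'approximately' with 'at least' in this one sentence. On-time doses then stay 24 hours apart, a moderately late dose is followed by the next at the usual hour, and a very late dose keeps a 12-hour gap.

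A fuller replacement also rules out a second dose on the same day:

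> Take no more than one dose per calendar day; after a late dose, take the next dose at the usual time provided at least 12 hours have passed, and otherwise as soon as 12 hours have passed.

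Use the same wording in subject training. The cost is a one-sentence amendment and the matching training text.

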**Study Visit 5, Cross-over, (Day 56) (+/- 1 week)**

Collect physical examination  
Collect Vital Signs measurements  
Chemistry Panel (sodium, potassium, chloride, bicarbonate, blood urea nitrogen, creatinine glucose)  
Liver Function tests (total bilirubin, direct bilirubin, alkalkine phosphatase, alanine aminotransferase, aspartate aminotransferase, lipase, amylase)

IRB Study Number: 20170189  
Version Date: June 16, 2021  
PI: [name]

NCT02889393

Plasma PK (Pharmacokinetics)

- Processed according to separate “Sample Processing Procedure”

Serum pregnancy test

Monitor severe adverse events (SAE) and adverse events (AE)

Collect Concomitant medication review

Collect Nutritional Assessment

3-day average fistula volume (3 days immediately preceding study visit)

Collect adjustment of medications and fluids if recorded

Fistula closure (y/n)

Complete Questionnaires (see additional documents)

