### **Events Necessitating Withdrawal from Study**

The occurrence of any of the following events may necessitate premature withdrawal of a subject from the study:

- Development of any of the following Inclusion/Exclusion criteria:
  - Significant, active, uncontrolled cardiac, hepatic, or renal dysfunction as defined by the Inclusion/Exclusion criteria
- New diagnosis of inflammatory bowel disease
- Use of any excluded medication
- Pregnancy
- Occurrence of a serious adverse event (SAE) thought to be related to study drug and not alleviated by symptomatic treatment
- Unwillingness to continue in the clinical study
- Death of the subject
- Principal Investigator decision (i.e. subject non-compliance with study procedures)
- Significant AE or medical decision that precludes the subject from adhering to study requirements

Readmission to the hospital for fistula-related complications (ex: cellulitis, intra-abdominal abscess, dehydration, etc.) is common and is likely to occur during the study treatment and follow-up period. Unless one of the above “Events Necessitating Withdrawal” occurs, the subject will remain enrolled in the study during hospitalization.

IRB Study Number: 20170189  
Version Date: June 16, 2021  
PI: [name]

NCT02889393

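### Surgical repair continues as standard of care in both periods, but the output endpoints have no rule for it, so an operative closure can score as response and cessation.

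*Combined protocol and SAP*

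**What the plan says.** **Treatment.** Section 5 (Drug Administration, Dispensation and Disposition) lists the components of standard of care (SOC) and ends with "careful fluid and electrolyte management, and occasionally surgical repair". It adds: "Subjects enrolled in this study will still receive SOC in addition to 8 weeks of teduglutide therapy". No component is withheld during the trial. Subjects are randomised "to begin teduglutide treatment immediately or to continue standard of care (SOC) treatment" and switch at day 56, so SOC, including repair, is available in both periods.

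**Endpoints.** Section 2 (Design) states: "The primary efficacy end point will be decrease in fistula volume by 20% from baseline 3-day average, as measured by the patient". It continues: "The secondary efficacy end points will be cessation of fistula output altogether", alongside questionnaire scores. Neither output endpoint refers to the cause of the fall.

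**Recording.** Study Visits 5, 10 and 11 each have one closure item, "Fistula closure (y/n"). The Data Fields list in Section 6 includes the number of days since the last operation, but no mode of closure and no date of a repair during the study.

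**Withdrawal.** The list in Section 9 (Events Necessitating Withdrawal from Study) does not name fistula surgery. It gives events that may lead to withdrawal, among them a decision by the principal investigator and "Significant AE or medical decision that precludes the subject from adhering to study requirements". For admissions for fistula-related complications, unless a listed event occurs, "the subject will remain enrolled in the study during hospitalization".

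**Analysis.** Section 7 plans a two-sample t-test on the baseline-to-final difference in volume. It has no rule for volumes or closures after an operation and no sensitivity analysis.

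**The concern.** The trial asks whether teduglutide reduces fistula output. A successful operation also takes output to zero, for a reason unrelated to the drug, and the endpoint definitions cannot tell the two apart. The operation is credited to whichever treatment the subject is on. In a teduglutide period it inflates the apparent drug effect; in an SOC period it inflates the control response.

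Two design features add to this. The trial is open label, so the decision to operate or to wait can depend on the known assignment. It is also a crossover with no separate period-2 baseline, so a repair in period 1 can affect what is scored in period 2.

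**Working it through.** There is no power or sample-size figure to reproduce: Section 7 says that none was calculated, and the planned size is 10.

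**Step 1. Score a successful repair by the stated rules.** Output after the repair is 0. The change from baseline B is (0 − B)/B = −100%, which meets the 20% criterion. Zero output also meets the cessation endpoint, and the closure item reads yes.

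**Step 2. Follow a period-1 repair into period 2.** If it holds and the enrolment baseline B is kept, the change in period 2 is still −100%, so the second treatment is credited too. If the day-56 volume were used as a new baseline, it would be 0 and a percentage change could not be calculated. The plan does not choose between these.

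**Step 3. Chance that the situation arises.** The documents give no repair rate, so the rate p per subject over 112/7 = 16 weeks is an assumption. With 10 independent subjects, P(at least one) = 1 − (1 − p)^10.

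| Assumed p | Calculation | P(at least one operation) |
|---|---|---|
| 1% | 1 − 0.99^10 | 10% |
| 2% | 1 − 0.98^10 | 18% |
| 5% | 1 − 0.95^10 | 40% |
| 10% | 1 − 0.90^10 | 65% |
| 20% | 1 − 0.80^10 | 89% |

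These count operations, not successful closures. They cover both periods together. At a constant hazard, the chance of at least one operation in a given 8-week period is 1 − (1 − p)^5: 5% at p = 1%, 23% at p = 5% and 67% at p = 20%.

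**Step 4. Effect on the rates.** One subject of 10 is 1/10 = 10 percentage points. This applies to a subject who is in the analysed 10 and would not otherwise have met the endpoint. For cessation, the exact 95% interval is 0% to 30.8% for 0/10 and 0.3% to 44.5% for 1/10.

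**Step 5. Effect on mean percentage change.** With k successful repairs and a common fall of f% in the others, the mean fall is [100k + f(10 − k)]/10.

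- f = 0, k = 1: 100/10 = 10%.
- f = 0, k = 2: 200/10 = 20%, equal to the hypothesised effect.
- f = 10, k = 1: (100 + 90)/10 = 19%.
- f = 10, k = 2: (200 + 80)/10 = 28%.

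The planned t-test is on volume, so its shift also depends on the operated subject's baseline output. These percentages show scale only and are not a result for that test.

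**The case against.** The strongest reply is that the plan nowhere says an operated fistula counts as a success. A reader might infer that it certainly would, or that surgery cannot lead to withdrawal. The documents support neither. The investigator-decision and medical-decision items could both cover a fistula operation, and a subject withdrawn before any dose might not be among the 10, who are defined as having received at least one. This stands and limits the claim to subjects who remain in the trial. It does not close the gap: the items are optional, would be applied with the assignment known, and do not say how an operated subject's data are scored.

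A reader might also take 40% to 89% as the likely chance of an affected subject. That needs a repair rate of 5% to 20%. The only guide in the text is that repair is occasional, and 1% to 2% fits that equally well, giving 10% to 18%. Nor is it supported that an operation sets output to zero permanently; no section says that repairs always succeed or last.

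Finally, because SOC runs in both periods, counting outcomes regardless of surgery is a legitimate target. A blanket non-response rule could also penalise a drug not yet given, or a subject who had already reached the 20% fall before the operation. These points stand and shape the fix. In a 10-subject pilot with roughly weekly output data, an operated case would probably be noticed. That lowers the urgency, but noticing a case is not a rule for scoring it.

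**Conclusion.** The point holds in a limited form. Under the plan as written, a successful fistula operation in a subject who is not withdrawn scores as response and cessation in the period in which it occurs. A period-1 repair that holds can also score in period 2 if the enrolment baseline is kept. The direction of bias is not fixed.

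The size rests on an assumed repair rate: 1% to 20% per subject gives a 10% to 89% chance of at least one operation among 10. The gap in the rule does not depend on that rate. The flaw is not fatal to a pilot, but the rule should be set before the data are seen, because a choice made afterwards in an open-label trial of 10 would be hard to defend. Whether surgery is permitted is a clinical matter and is not in question here.

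**What to change.** In Sections 2 and 7, state that:

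- a fistula operation counts as non-response, and not as cessation, for the period in which it occurs;
- volumes after the operation are not used in the volume comparison;
- a period that follows an operation in the earlier period is not evaluable for output, rather than a non-response.

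Add two sensitivity analyses. One uses the last 3-day average before the operation, which protects a subject who had already responded. The other counts outcomes regardless of surgery.

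Replace the yes/no closure item at Visits 5, 10 and 11 with none, spontaneous or operative, and record the date.

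The cost is one analysis rule, two short sensitivity analyses and a revised case report form item; clinical care is unchanged. Response and cessation rates may be slightly lower, and period-2 output data are lost for anyone operated on in period 1.
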